**5.5 Description of Intervention**

The intervention will include the following two components: 1) assessing and treating sexual dysfunction in the transplant clinic; and 2) referring patients with more complicated needs to the sexual health clinic. During the first component, patients will attend up to two intervention visits with the trained transplant clinicians to assess and address sexual dysfunction. If patients do not respond to the intervention delivered in the transplant clinic and/or they are deemed to have more complex sexual health needs, they will be referred to the sexual health clinic for additional expertise (second component). Therefore, the intervention entails both the intervention visits in the transplant clinic as well as any additional visits in the sexual health clinic.

- 1. Primary sexual dysfunction intervention in the transplant clinic:** We developed this multimodal intervention in collaboration with [name] based upon 1) a comprehensive review of the NCCN guidelines on survivorship; and 2) a systematic review of the literature on sexual dysfunction affecting men and women.

We will schedule all consented participants for a clinic visit with one of the three trained transplant clinicians specifically addressing sexual dysfunction, including the following elements:

- A. In-depth sexual function assessment:** The trained transplant clinicians will conduct a comprehensive sexual function assessment based on the NCCN survivorship guidelines. They will utilize the baseline questionnaires completed by participants to identify factors contributing to sexual dysfunction. Female participants will complete the Female Sexual Function Index (FSFI) and male participants will complete the PROMIS Sexual Function and Satisfaction measures for men. Additionally, the transplant clinicians will evaluate psychological causes for sexual dysfunction including self-confidence, body image issues, anxiety, and depression. Lastly, the transplant clinicians will evaluate patients for hormonal deficiencies,

Sexual Dysfunction Intervention Post-Bone Marrow Transplant  
Protocol version 7/02-28-2017

GVHD affecting the skin and genitals, medication side-effects or substance abuse, and other comorbidities that may affect sexual function in men and women.

- B. **Normalization, Empowerment, and Education:** The transplant clinicians will provide information about sexuality in order to normalize these issues and affirm the importance of the topic. In addition, the transplant clinicians will educate patients on issues relevant to sexual health, including but not limited to the prevalence of sexual dysfunction post HCT. They will also elicit participants' concerns regarding engaging in such a conversation. They will provide participants with educational materials focusing on sexual dysfunction in cancer survivors including the potential etiologies and contributing factors as well as helpful suggestions for management. The transplant clinicians will empower patients to ask questions and utilize these resources.
- C. **Therapeutic Interventions:** Additional interventions instituted in the transplant clinic will be directed towards the various etiologies affecting sexual function. Additional intervention visits may also be conducted over the phone to minimize the stress and travel of participants. Specifically:

**For men with:**

- Signs and symptoms suggestive of testosterone deficiency: These include erectile dysfunction, low sexual desire, and delayed ejaculation, as well as other signs such as visceral obesity, reduced muscle mass, and low bone mineral density. Transplant clinicians will screen for testosterone deficiency. If total testosterone <230 ng/dL, they will start testosterone supplementation.
- Erectile dysfunction: Transplant clinicians will counsel male participants regarding risk factor modification including smoking cessation, weight loss, increasing physical activity, and avoiding access alcohol consumption. In addition, the transplant clinicians will prescribe and titrate phosphodiesterase inhibitors for the treatment of erectile dysfunction.

**For women with:**

- Signs and symptoms suggestive of menopause or treatment-induced amenorrhea: These include vaginal symptoms, including dryness and dyspareunia, as well as more systemic signs, such as hot flushes and irritability. If present, transplant clinicians will offer participants hormone replacement therapy. However, acknowledging that some patients will not be interested in hormone replacement therapy, transplant clinicians will offer non-estrogenic therapies including gabapentin and/or selective serotonin inhibitors.
- Dyspareunia: Patients will require a pelvic examination for complaints of dyspareunia and they will be referred to the sexual health clinic.

**For men and women with:**

- Skin GVHD: Transplant clinicians will treat signs of genitopelvic GVHD with local corticosteroid and/or tacrolimus creams.
- Medication-induced sexual dysfunction: Transplant clinicians will identify potential offending agents and discontinue them if possible. When medications causing sexual dysfunction are necessary, the clinicians will prescribe treatment to enhance sexual function such as phosphodiesterase inhibitors.
- Low desire secondary to depression treatment: Patients on antidepressant medication may experience a lack of desire. For these patients, transplant clinicians will offer the use of phosphodiesterase inhibitors.

We will schedule all participants for a 4-week follow-up intervention visit and/or referral to the MGH Cancer Center sexual health clinic (see specialty referral to the sexual health clinic). The objective of the 4-week follow-up visit is to assess participants' responses to specific therapies. 4-week follow-up visits can be conducted over the phone or in clinic at MGH. If participants do not report any improvement in their sexual dysfunction during the follow-up visit based on the transplant clinician's assessment, they will be considered non-responders. The transplant clinicians will then refer them to the sexual health clinic within 30 days.

2. ***Specialty referral to the sexual health clinic:*** During the first transplant clinic visit, the transplant clinicians will refer the following participants directly to the MGH Cancer Center sexual health clinic:
- Suspected psychological etiology for sexual dysfunction (self-confidence, body-image issues, depression, anxiety, and/or fear of disease recurrence).
  - Suspected relationship and intimacy problems.
  - Women participants with vaginal dryness, itching, and/or pain with intercourse: These women will require a vaginal examination to differentiate atrophic vaginitis from GVHD.
  - Participants with complex sexual needs as determined by the transplant clinicians.

[name] will evaluate all participants referred to the sexual health clinic at the MGH Cancer Center. He will conduct a comprehensive sexual assessment and individualize his treatment approach based on the needs of the study participants. Possible interventions will include: the use of lubricants, vaginal moisturizers, topical lidocaine, estrogen creams for atrophic vaginitis, local corticosteroid therapy for GVHD, dilators, testosterone to enhance male/female sexual desire, continuous and intermittent phosphodiesterase inhibitors, vacuum-assisted erection devices, penile self-injections, intraurethral prostaglandins, and referrals for penile prosthesis. Moreover, [name] will triage and refer participants with psychological causes of sexual dysfunction to psychiatry, cognitive behavioral therapy, and/or couples or sex therapy as appropriate.

## **5.6 Data Collection**

As discussed previously in section 5.4 (Administration and timing of self-reported measures), we will collect and enter all patient-reported data electronically using Research Electronic Data Capture (REDCap). Our research team has extensive experience using REDCap and will create and design the surveys in a web browser, with institutional information technology support. The REDCap Survey system offers secure, HIPAA compliant, web-based applications that provide an intuitive interface for participants to enter data, with real-time validation rules (automated data type and range checks) at the time of entry.

## **5.7 Description of Study Process**

### **5.7.1 Study Instrument Administration**

Patients will use tablet computers to complete baseline and 6-month questionnaires in clinic. If participants refuse or are unable to complete the questionnaires on the computer, they will be permitted to use paper versions. Participants who are not present in the cancer center during the period of data collection will be provided with remote access to the REDCap system or paper-based questionnaires for home administration. The research team will contact patients twice to remind them to complete and return the surveys. If study participants fail to complete the surveys within the expected time point, we will report the data as missing and document the reason for incompleteness.

### **5.7.2 Intervention Administration**

## Sexual Dysfunction Intervention Post-Bone Marrow Transplant Protocol version 7/02-28-2017

Patients will be scheduled to meet with the trained transplant clinician for the sexual dysfunction intervention on the same day as their regularly scheduled follow-up visit. After the initial intervention visit, the participants will be scheduled for a 4-week follow-up visit with the trained transplant clinician and/or referral to the sexual health clinic. The objective of the 4-week follow-up visit is to assess participants' responses to specific therapies. If participants do not report any improvement in their sexual dysfunction during the follow-up visit based on the transplant clinician's assessment, they will be considered non-responders. The transplant clinicians will then refer them to the sexual health clinic within 30 days. Once referred to the sexual health clinic, patients and [name] may schedule additional visits as needed.

### *5.7.3 Special Concerns*

We do not anticipate any complications with this study. We have administered questionnaires to over 100 patients in previous studies and there have been no complications.

### *5.7.4 Compensation*

We will provide no compensation for participating in this study.

## **5.8 Adverse Reactions and Their Management**

### *5.8.1 Reporting Adverse or Unanticipated Events*

This study is evaluating the feasibility and preliminary efficacy of a sexual dysfunction intervention with minimal chance of causing harm. We have administered study questionnaires to over 100 patients in previous studies with no adverse events. While some of the items on the questionnaires are sensitive in nature, no previous study participants have withdrawn from the study.

### *5.8.2 Anticipated Reactions*

Should participants exhibit or express distress or anger, they will be reassured by the Research Assistant that they need not answer any questions which they find upsetting. They will also be reminded that study participation is voluntary. If participants remain distressed, both the Principal Investigator and the transplant oncology team will be notified. Should several participants express distress over an individual item, the research team will review the questionnaire and contact the IRB to consider removing it from the study.

If participants report severe distress or suicidal ideations during the interview or while completing any of the questionnaires, the research team will inform the participants that there is an obligation to report this to the patients' primary oncology team and the transplant social worker. The oncologist and social worker will then determine the need to involve psychiatry and take further action as deemed necessary. The research team will review sensitive items regarding suicidal ideations immediately at the time of survey administration and will report any suicidal ideations to the oncology provider and social worker promptly prior to participants' departure from clinic.

### *5.8.3 Reaction Management*

Should participants experience distress, the outpatient transplant social worker will be contacted to see the participant. All staff are familiar with how to contact the social worker via pager. The transplant social workers at MGH have all agreed to be available to respond and help with the management of any adverse reactions.

If participants report suicidal ideations during the interview or while completing any of the questionnaires, the research team will inform study participants that there is an obligation to inform their oncologist and the

transplant social worker. The oncologist and social worker will then determine the need to involve psychiatry and take further action as deemed necessary.

## 6 Ethical and Legal Issues

### 6.1 Confidentiality

All patient information will remain confidential and stored on Partners computers and in REDCap. Identifiers such as name will only be used during the initial data retrieval process and can be destroyed once all data records have been obtained and data analysis completed.

Participants' response to survey questions will remain confidential unless there are active suicidal ideations confirmed by the research team. Under these circumstances, as clearly stated in the patient consent form, participants will be informed that the research team has a formal obligation to inform the oncologist and the transplant social worker due to concern for participants' safety. The oncologist and the social worker will then determine the need to involve psychiatry and/or take further action as deemed necessary.

## 7 Statistical Analysis

### 7.1 Primary and secondary endpoints:

7.1.1 *Primary endpoint:* The primary endpoint of the proposed study is feasibility. We chose the sample size for this study based on the feasibility of completing the project during the proposed timeframe. The proposed intervention will be deemed feasible if it meets the following criteria:

- At least 75% (95% confidence interval +/- 12%) of patients screening positive for sexual dysfunction causing distress agree to participate in the study and attend the first scheduled intervention visit.
- At least 80% of participants (95% confidence interval +/- 11%) attend at least two intervention visits (either in the transplant clinic or specialty referral).

7.1.2 *Secondary endpoint:* The following secondary endpoints represent the preliminary efficacy endpoints

1. Change in sexual function from baseline to 6 months
2. Change in QOL from baseline to 6 months
3. Change in psychological distress scores (HADs and PHQ-9) from baseline to 6 months
4. To qualitatively 1) explore patients' perception of the acceptability and content of the sexual dysfunction intervention; 2) explore patients' perception of the efficacy; and 3) identify the optimal timing of intervention delivery during the survivorship course.

## 7.2 ***Sample Size Calculation:***

As stated in section 7.1.1, the primary endpoint of the proposed study is feasibility. We chose the sample size for this study based on the feasibility of completing the project during the proposed timeframe. The proposed intervention will be deemed feasible if it meets the following criteria:

- At least 75% (95% confidence interval +/- 12%) of patients screening positive for sexual dysfunction causing distress agree to participate in the study and attend the first scheduled intervention visit.
- At least 80% (95% confidence interval +/- 11%) of participants who attend the first visit will also attend at least one additional follow-up visit and/or specialty referral.

These estimates are informed by our prior supportive care trial in HCT patients. We are currently conducting a study evaluating a palliative care intervention for patients undergoing HCT. In this study, we have successfully enrolled 40/44 (90.9%) of potentially eligible participants. Only one participant withdrew and did not complete the longitudinal follow-up (2.5%). Given the sensitive nature of the topic, we are making a conservative estimate of feasibility that 60% (0.75 X 0.80) of patients screening positive for sexual dysfunction will attend the first scheduled intervention visit and at least one additional follow-up and/or specialty referral visit.

We will also select approximately 8 male and 8 female patients from the phase I participant pool to participate in the qualitative phase of this study. We chose approximately 8 male and 8 female patients for the qualitative study to ensure that we have sufficient number of patients to achieve thematic saturation. Additionally, we will purposefully select participants with varying times from their HCT to capture participants throughout the survivorship trajectory. Therefore, we will select approximately 5-6 participants who enrolled in the study within each of the following timeframes: 1) less than one year after HCT; 2) greater than one year, but less than two years after HCT; and 3) more than two years after HCT.

7.3 ***Stratification factors and intervention allocation plan for randomized studies:*** not applicable

7.4 ***Definition of an allowance in design for unevaluable/ineligible participants:*** No applicable

7.5 ***Analysis Plan:***

We will report baseline demographic and clinical characteristics of all study participants. The primary endpoint of the proposed study is feasibility. The proposed intervention will be deemed feasible if it meets the following criteria:

- At least 75% of patients screening positive for sexual dysfunction causing distress agree to participate in the study and attend the first scheduled intervention visit.
- At least 80% of participants who attend the first visit will also attend at least one additional follow-up visit and/or specialty referral.

The secondary endpoints will include determining the preliminary efficacy of the intervention in improving QOL, mood, and sexual dysfunction (objective 2). We will utilize the paired t-test to examine changes in QOL (FACT-BMT), depression and anxiety (HADS, PHQ-9), and sexual dysfunction (PROMIS for males, and FSFI for females) scores from baseline to 6 months after initial intervention visit. In addition to examining

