## **2 Objectives**

### *Quantitative Objectives and Hypotheses:*

- 1. To evaluate the feasibility of implementing a multi-modality sexual dysfunction intervention for allogeneic HCT survivors.**

*Hypothesis: We will be able to recruit 75% of patients who screen positive for sexual dysfunction causing distress to participate in a sexual dysfunction intervention, and 80% of participants will attend at least one additional follow-up or referral visit.*

- 2. To determine the preliminary efficacy of the intervention in improving sexual function, QOL, and mood.**

*Hypothesis: Participants will have improved sexual function, QOL, and mood at 6 months post-intervention compared to baseline.*

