## **5.2 Study Procedures:**

We will recruit 53 patients with hematologic malignancies 3 months after allogeneic HCT who report having sexual dysfunction causing distress for this study. Once written informed consent is obtained, patients will receive an outpatient multimodal sexual dysfunction intervention. The interventionist will rescreen the patients at the beginning of their initial visit. If patients no longer experience sexual dysfunction before their initial study visit, they will be considered ineligible for the study as they are no longer experiencing distress relating to sexual dysfunction. Because these patients have already signed consent, they will count towards accrual, but will no longer be eligible to participate in the intervention.

Prior to patients' enrollment on this study, we will train a total of two transplant clinicians regarding how to assess and address sexual dysfunction in the transplant clinic. [name] is the Director of the MGH Cancer Center Sexual Health Clinic and a world-renowned expert on sexual dysfunction in cancer survivors. He will first provide transplant clinicians with reading materials regarding how to assess and address sexual dysfunction. The transplant clinicians will review this literature prior to their didactic training sessions with [name]. [name] will then conduct two training sessions with the same two transplant clinicians prior to study enrollment to ensure they acquire the necessary skills to implement the sexual dysfunction intervention in the transplant clinic. One transplant MD and one experienced transplant nurse practitioner (NP) will be responsible for implementing the intervention in the transplant clinic.

[name] will first conduct a two-hour didactic training session with the transplant clinicians, focusing on the following areas:

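### The second feasibility criterion has two different denominators, and the stated ±12% and ±11% do not fit the nested denominators of Section 7.2

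*Combined protocol and SAP*

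**What the plan says.** The intervention is called feasible if two criteria are met.

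Criterion 1 (Section 7.2) is a share of screen-positive patients: "At least 75% (95% confidence interval +/- 12%) of patients screening positive for sexual dysfunction causing distress agree to participate in the study" and come to the first intervention visit.

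Criterion 2 appears four times:

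- Section 2: "80% of participants will attend at least one additional follow-up or referral visit".
- Section 7.1.1: "At least 80% of participants (95% confidence interval +/- 11%) attend at least two intervention visits".
- Section 7.2: "At least 80% (95% confidence interval +/- 11%) of participants who attend the first visit will also attend" a further follow-up or referral visit.
- Section 7.5: "At least 80% of participants who attend the first visit will also attend at least one additional follow-up visit and/or specialty referral".

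Section 7.2 then chains the two criteria: "we are making a conservative estimate of feasibility that 60% (0.75 X 0.80", expressed as a share of screen-positive patients.

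On who is counted, Section 4.1 has 53 patients taking part and registers them after consent and baseline questionnaires, before any intervention visit. Section 5.5 schedules every consented participant for that first visit. Section 5.2 adds: "The interventionist will rescreen the patients at the beginning of their initial visit". Those who no longer report the problem become ineligible, but "Because these patients have already signed consent, they will count towards accrual, but will no longer be eligible to participate in the intervention". Section 7.4 makes no allowance for such patients. Neither interval has an n attached to it.

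**The concern.** There are two problems, and the first matters more.

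1. **Denominator.** Sections 2 and 7.1.1 count all participants, while 7.2 and 7.5 count only those who attended the first visit. Sections 4.1 and 5.5 treat patients as participants before that visit, and Section 5.2 expects some consented patients not to go on to the intervention. The two groups can therefore differ in size, and the primary endpoint could pass under one section and fail under another on the same data. The plan also does not say whether a patient who comes to the first visit and fails the rescreen has attended it.

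2. **Precision.** Criterion 2 is stated with the narrower interval (11 against 12 points). Under the chain in 7.2 its denominator is only three quarters of criterion 1's, which should make its interval the wider one.

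**Working it through.** **Inputs.** Thresholds 75% and 80%, half-widths 12 and 11 points, and the product 0.75 × 0.80 (Section 7.2); 53 patients (Sections 3.1 and 4.1); accrual counted at consent (Section 5.2). Formula: half-width = 1.96 × √(p(1−p)/n).

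**Step 1: reproduce the stated half-widths.** With n = 53 for both criteria:

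- 1.96 × √(0.75 × 0.25/53) = 11.66%, which rounds to 12%.
- 1.96 × √(0.80 × 0.20/53) = 10.77%, which rounds to 11%.

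Both figures are recovered. The n is not unique: ±12% at 75% fits n = 47 to 54, ±11% at 80% fits n = 47 to 55, so any common n from 47 to 54 works.

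**Step 2: apply the nesting of Section 7.2.** Let n1 be the screen-positive patients and n2 = 0.75 × n1 the first-visit attenders. The ratio of half-widths, criterion 2 to criterion 1, is

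√[(0.16/0.75)/0.1875] = 1.067, whatever n1 is.

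Criterion 2's half-width always exceeds criterion 1's, so it cannot round to a smaller figure. To get 12% and 11% from different denominators would need at most 54 screen-positive patients and at least 47 attenders, a share of at least 47/54 = 87%, not 75%. Continuity-corrected, Wilson and Clopper-Pearson intervals gave no nested pair that fits either.

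**Step 3: range of correct values.** Because the 53 are counted at consent, n1 is at least 53 and n2 at most 53. With n2 = 0.75 × n1:

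| First-visit attenders (n2) | Screen-positive (n1) | Criterion 1 | Criterion 2 |
|---|---|---|---|
| 53 | 70.7 | ±10.1% | ±10.8% |
| 48 | 64 | ±10.6% | ±11.3% |
| 44 | 58.7 | ±11.1% | ±11.8% |
| 39.75 | 53 | ±11.7% | ±12.4% |

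From 41 to 46 attenders, criterion 1 rounds to 11% and criterion 2 to 12%, so neither stated figure holds. The largest departures are 12 − 10.1 = 1.9 points and 12.4 − 11 = 1.4 points.

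**Step 4: effect of the denominator on the verdict.** Take participants to be all 53 consented. Section 7.1.1 then needs 0.8 × 53 = 42.4, that is 43 patients with a second visit. The attender numbers are assumed for illustration.

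| First-visit attenders | Needed under 7.2/7.5 | Counts that pass 7.2/7.5 but fail 7.1.1 | Criterion 1 also met if screen-positive number at most |
|---|---|---|---|
| 53 | 43 | none | 70 |
| 52 | 42 | 42 | 69 |
| 50 | 40 | 40–42 | 66 |
| 48 | 39 | 39–42 | 64 |

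For example, 40/50 = 80.0% but 40/53 = 75.5%. The last column is attenders/0.75, rounded down; within those limits criterion 2 alone decides the primary endpoint.

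**Step 5: rescreen failures.** Suppose 53 patients come to the first visit, 3 fail the rescreen, and 70 had screened positive (assumed). Criterion 1 is 53/70 = 75.7% if the three count as attending, 50/70 = 71.4% if they stay in the denominator only, and 50/67 = 74.6% if they are removed from both. Criterion 2's denominator is 53 or 50 even under the 7.2 wording, with the same split at 40 to 42.

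**The case against.** The best reply is that there is one criterion, loosely worded. Section 2 speaks of an additional visit, which presupposes a first. In 7.1.1 the second bullet's participants can be read as those who met the first bullet. Section 7.2 refers back to 7.1.1 as if the two agreed, and the analysis plan in 7.5 is explicit. That reading is possible, but it is nowhere stated. The word *additional* fixes the numerator only: a patient who misses the first visit still counts as a failure if included among participants. Section 5.5 also uses the term for consented patients who have not yet been seen.

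A second reply is that Section 5.2 makes rescreen failures ineligible, so they would not naturally count as participants in criterion 2. This has force. If they are excluded, only no-shows can separate the two wordings. It leaves open how they count in criterion 1 and whether coming in to be rescreened is attendance.

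A third reply is that the half-width error changes nothing. It is small, the sample size was set by the timeframe, and with 47 to 53 attenders criterion 2 still rounds to ±11% while criterion 1 is tighter than stated. This is correct, and it makes the precision point secondary. The stated pair is still inconsistent with the plan's own structure.

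**Conclusion.** The concern holds on both parts. Criterion 2 has two denominators, and the choice can reverse the primary conclusion once at least one of the 53 misses the first visit. The window is one count with 52 attenders, three with 50 and four with 48. This assumes that participants means all consented patients. There is no conflict if all 53 attend, and a smaller one if rescreen failures are excluded.

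The stated ±12% and ±11% cannot both be right under the nesting in 7.2. The correct pair lies between ±10.1%/±10.8% and ±11.7%/±12.4%, depending on what 53 counts. That the authors used one n of about 53 for both is a likely explanation, not something the documents say. The half-width error affects neither the observed-proportion rule nor the choice of 53. The denominator is the reason to amend the text, and it should be settled before the data are analyzed.

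**What to change.** - Use first-visit attenders as the denominator of criterion 2, as in 7.2 and 7.5 and as the 60% product requires, and carry that wording into Sections 2 and 7.1.1.
- In 7.5, state for each criterion whether rescreen failures are in the denominator, and whether being rescreened at the initial visit counts as attending it.
- In 7.1.1 and 7.2, give the expected n for each criterion and compute each half-width from it. If all 53 are expected to attend, this is about 71 screen-positive patients with ±10% and 53 attenders with ±11%. If fewer attend at the planned 75%, both widen; with 48 attenders they are ±10.6% and ±11.3%.

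The cost is a few lines of text and two figures. Enrollment of 53, the 75% and 80% thresholds and the study procedures do not change.
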